9.1.1. Inclusion criteria

Patients must meet all of the following inclusion criteria to be eligible for inclusion in the study:

090177e19b7d94e0\Approved\Approved On: 29-Aug-2023 01:40 (GMT)

Apixaban

B0661183 NON-INTERVENTIONAL STUDY PROTOCOL

Protocol Version: 2.0 29 July 2022

1. Patients with ≥ 1 diagnosis code for VTE (inpatient [primary or secondary discharge diagnosis] or any position on an outpatient non-ancillary medical claim) between January 1, 2017 and October 31, 2021 (selection window).
 - Note: Qualifying outpatient encounters followed by qualifying inpatient encounters within 7 days will be considered an inpatient VTE event, unless LMWH or apixaban was initiated between encounters, in which case it will be classified as an outpatient VTE event
 - First date of claim with a VTE diagnosis code will be termed the ‘index VTE encounter’

2. Evidence of having active cancer, defined as ≥ 2 medical claims with a cancer diagnosis (excluding nonmelanoma skin cancer) on different days during the 6 months before or within 30-days after the index VTE event

OR

≥ 1 medical claim for a cancer diagnosis AND ≥ 1 claim for cancer treatment (eg: chemotherapy, radiation, immunotherapy, hormone therapy or cancer related surgery using national drug codes (NDC), international classification of diseases, tenth revision, clinical modification [ICD-10-CM] procedure codes or healthcare common procedure coding system [HCPCS] codes) during 6 months before or within 30 days after the index VTE encounter

3. ≥ 1 claim of apixaban or LMWH (dalteparin orenoxaparin) on or within 30 days following the index VTE encounter.
 - a. The date of the first apixaban or LMWH prescription fill will be designated as the index date
4. ≥ 12 months of continuous enrollment prior to the index date (pre-index)
5. ≥ 1 months of continuous enrollment including and following the index date (post-index)
 - a. Note: Each patient will have a variable follow-up period with a minimum of 1-month follow-up. Patients will be followed from the day after the index date through the earliest of the following: health plan disenrollment, index therapy discontinuation, switch to another anticoagulant, or study end (December 31, 2021).
 - b. Discontinuation will be defined as occurrence of a ≥ 30 day gap from the run-out of days’ supply of the index LMWH or apixaban prescription. The date of the discontinuation will be defined as the last day of the days’ supply of the last filled prescription.

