9.3.2. All-cause HCRU and Costs Over the Post-Index Period (Post-IPTW)

All-cause HCRU and costs will be reported for the Apixaban and LMWH cohorts over the variable post-index period (minimum 1 month enrollment), post-IPTW. Costs will be reported

PFIZER CONFIDENTIAL

CT24-WI-GL02-RF02 4.0 Non-Interventional Study Protocol Template For Secondary Data Collection Study 01-Jun-2022

Page 23 of 35

090177e19b7d94e0\Approved\Approved On: 29-Aug-2023 01:40 (GMT)

Apixaban

B0661183 NON-INTERVENTIONAL STUDY PROTOCOL

Protocol Version: 2.0 29 July 2022

as per patient per month (PPPM). Over the post-index period, a 30 day period will be used (to represent a month) to ‘standardize’ the period of time for which costs and HCRU will be reported. For each patient, costs will be divided by the variable post-index period in total-person days and then multiplied by 30 to calculate PPPM costs. For example, if a patient has total costs of \$10,000 with 60 days of follow-up, the PPPM will be calculated as $(\$10,000/60) * 30 = \$5,000$.

HCRU will be expressed as both the proportion of patients with such utilization (e.g., the percentage of patients with at least one pharmacy claim, the percentage of patients with at least one physician office visits, etc.) as well as per-patient mean, SD, median and IQR number of visits/services. Costs will be expressed as per-patient mean, SD, median and IQR. Utilization and costs will be calculated on a per patient basis, averaged across the cohort. The denominator will include all patients in the cohort. Costs will be converted to 2021 US dollars (USD) using the medical component of the Consumer Price Index.

HCRU and costs will be reported for mutually exclusive categories: outpatient pharmacy, inpatient hospitalizations, and outpatient care. Outpatient care will comprise the following categories: ER visits, outpatient physician office visits, outpatient surgical visits, laboratory and pathology, radiology and all other services.

All-cause HCRU and costs will be reported for each of the following services:

- Pharmacy
 - Patients with ≥ 1 prescription fill (n, %)
 - Number of prescription fills per patient (mean, SD, median, IQR)
 - Total pharmacy cost per patient (mean, SD, median, IQR)
- Outpatient Services
 - Total outpatient medical care cost per patient (mean, SD, median, IQR)
 - Physician office visits
 - Patients with ≥ 1 physician office visit (n, %)
 - Number of physician office visits per patient (mean, SD, median, IQR)

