CT24-WI-GL02-RF02 4.0 Non-Interventional Study Protocol Template For Secondary Data Collection Study 01-Jun-2022

Page 26 of 35

090177e19b7d94e0\Approved\Approved On: 29-Aug-2023 01:40 (GMT)

Apixaban

B0661183 NON-INTERVENTIONAL STUDY PROTOCOL

Protocol Version: 2.0 29 July 2022

- Number of CRNM bleeding events (denoted by inpatient or outpatient events that meet the definition above) (mean, median, SD, IQR)
- Time (in days) from index date to first CRNM bleeding event (mean, median, SD, IQR)

The Cost, and HCRU, for each event will be defined as the cost associated with the hospitalization for the respective event (i.e., recurrent VTE, MB, or CRNM bleeding) as well as all subsequent event-related medical costs (pharmacy costs will not be included). These can be determined via an appropriate diagnosis code that relates to the event of interest. Major bleeding-related medical costs will be defined as costs associated with the first major bleeding hospitalization plus all subsequent bleeding costs occurring in the inpatient (primary or secondary diagnosis) or outpatient setting (any position). Recurrent VTE-related medical costs will be defined as the costs associated with the first recurrent VTE hospitalization plus all subsequent VTE costs in the inpatient (primary or secondary diagnosis) or outpatient (any position) setting. Similarly, CRNM bleeding-related medical costs will be defined as hospitalization costs or outpatient costs associated with the first CRNM bleeding as defined above and all the subsequent CRNM bleeding costs in the inpatient (primary or secondary diagnosis) or outpatient (any position) setting.

The outpatient services and inpatient hospitalization HCRU and cost variables presented in section 8.3.2 will also be reported for recurrent VTE-related, major bleeding-related and CRNM bleeding-related utilization and costs.

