9.7. Data analysis

Descriptive statistics will be produced for all relevant study measures previously described, for the 2 therapy cohorts of interest. Categorical measures will be presented using frequency (number of patients [n]) and percentage (%) of total study patients observed in each category. Continuous and count variables will be presented as the mean, SD, median and IQR. As relevant, continuous variables will also be categorized into intervals.

Stabilized IPTW will be used to balance patient characteristics between apixaban and LMWH cohorts.^{11,12} Weights will be constructed by estimating each subject's probability of receiving treatment based on covariates. For comparisons of baseline characteristics between the apixaban and LMWH cohorts, both pre- and post-IPTW, standardized mean difference (SMD) will be calculated to evaluate the difference in baseline covariates between cohorts. SMD is calculated as the difference in means or proportions of a variable divided by the pooled standard deviation. SMD of ≥ 0.10 between groups is considered meaningful.¹³ For comparisons of events and HCRU/cost over the variable post-index period post-IPTW, comparisons will be conducted using weighted chi-square tests for categorical variables and weighted t-tests (mean) for continuous variables (note there is no corresponding weighted test for the median). Comparisons between independent samples (e.g., among patients with ≥ 1 hospitalization) and pre-IPTW samples will be conducted using the parametric t-test (mean) and non-parametric Wilcoxon rank-sum test (median) for continuous variables; data will be reported for the unweighted sample. A p-value < 0.05 will be considered statistically significant. However, to account for multiple comparisons, a Bonferroni correction may be implemented such that the critical p-value ($p < .05$) may be divided by the number of comparisons (i.e., 3 comparisons, in order to yield a new critical p-value, $.05/3 = 0.0167$). Analyses will be conducted using SAS[®] (statistical analysis software) Release 9.4 (SAS Institute Inc., Cary, NC).

IQVIA will develop up to 4 multivariable analysis models, to be mutually agreed upon Pfizer/BMS and IQVIA. For example these may include weighted generalized linear models (GLM) with log transformation and gamma distribution to estimate adjusted (all-cause) cost ratio

PFIZER CONFIDENTIAL

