CT24-WI-GL02-RF02 4.0 Non-Interventional Study Protocol Template For Secondary Data Collection Study 01-Jun-2022

Page 29 of 35

090177e19b7d94e0\Approved\Approved On: 29-Aug-2023 01:40 (GMT)

Apixaban

B0661183 NON-INTERVENTIONAL STUDY PROTOCOL

Protocol Version: 2.0 29 July 2022

between the two cohorts. A negative binomial distribution may be developed to estimate adjusted visits such as physician office visits, emergency room visits or other HCRU. Two-part regression analyses will be used to evaluate the impact of the LMWH treatments relative to apixaban on recurrent VTE-related, major bleeding-related, CRNM-related medical HCRU or costs. The 2-part regression analyses¹⁴ will be used to avoid the analytical issues associated with the large number of data with 0 values for HCRU and costs for VTE-related, major bleeding-related, CRNM related HCRU and costs. In the two-part model, first the probability of observing a positive versus zero outcome will be determined using a binary choice model. In the second part of the model, conditional on a positive outcome, an appropriate regression model such as a GLM model for costs or a negative binomial model for HCRU will be fit for the positive outcome. Covariates to be considered for inclusion into the models will include demographic and clinical characteristics of interest guided by the univariate findings. These candidate variables will be considered and retained in the model if significant ($SMD \geq 0.10$) using a stepwise approach. Collinearity among the variables of interest will be evaluated during model development.

Any major modifications of primary endpoint definitions or their analyses would be reflected in a protocol amendment.

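### The two-part HCRU model names no zero truncation, variance estimator or combined per-patient effect; with ordinary negative binomial defaults its intervals would be wrong

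*Combined protocol and SAP*

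**What the plan says.** Section 9.7 applies two-part regression to estimate the effect of LMWH relative to apixaban "on recurrent VTE-related, major bleeding-related, CRNM-related medical HCRU or costs", because many patients will have zeros. In part one, "first the probability of observing a positive versus zero outcome will be determined using a binary choice model"; no link is named. In part two, restricted to patients with a positive value, the plan calls for "an appropriate regression model such as a GLM model for costs" or, for use of services, says that "a negative binomial model for HCRU will be fit for the positive outcome".

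Section 9.7 does not mention a zero-truncated distribution, the variance estimator for either part, or a step that turns the two parts into one mean, difference or ratio per patient.

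Outside the model, 9.3.2 says of HCRU and costs that "The denominator will include all patients in the cohort". Section 9.3.3 adds that the same outpatient and inpatient variables "will also be reported for recurrent VTE-related, major bleeding-related and CRNM bleeding-related utilization and costs". Section 9.7 compares post-IPTW results with "weighted t-tests (mean) for continuous variables (note there is no corresponding weighted test for the median").

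On follow-up, 9.1.1 states: "Each patient will have a variable follow-up period with a minimum of 1-month follow-up". Section 9.3.2 uses a 30-day unit for reporting, but 9.7 does not say how follow-up time enters a count model.

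**The concern.** There are two gaps.

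**Standard errors for positive counts.** A count restricted to positive values starts at 1. An ordinary negative binomial puts probability on zero and cannot have a variance below its mean. When most positive counts are 1, the real variance is far below the mean, the dispersion estimate falls to zero, and the fit becomes a Poisson with too large a standard error. When counts are high and overdispersed, the error runs the other way. One default model would then be conservative for repeat hospitalizations and too liberal for frequent services.

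**No combined effect.** The objectives compare HCRU and costs between the cohorts, and 9.3 says that outcomes will be evaluated after both IPTW and GLM adjustment. Two separate coefficients, one for having any event-related use and one for the amount among users, do not give that comparison and may point in opposite directions. This gap reaches event-related costs, a primary objective, as well as HCRU.

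**Working it through.** **The plan's own figure.** No size is stated for the two-part model. The only computed figure is the sample size in 9.5. With the pooled two-proportion formula, two-sided 5%, 80% power and no continuity correction,

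n = [1.960·√(2p̄(1−p̄)) + 0.842·√(p₁(1−p₁)+p₂(1−p₂))]² / (p₁−p₂)².

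- 5.6% vs 7.9%: n = 1,867, as stated.
- 148/3,393 vs 396/6,108: n = 1,788, as stated.

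These rates give a plausible number of patients in part two for recurrent VTE at the minimum size: 1,788 × 4.362% = 78 and 1,788 × 6.483% = 116.

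**Standard error for positive counts.** The documents give no distribution of event-related counts, so the latent mean μ and dispersion a are assumptions. For a zero-truncated negative binomial, with p₀ = (1+aμ)^(−1/a):

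- mean of positives m = μ/(1−p₀)
- variance of positives v = [μ+μ²(1+a)]/(1−p₀) − m²

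With two groups and no covariates, the ordinary fit returns the log ratio of the two means. With K = 1/78 + 1/116 = 0.02144 and fitted dispersion α:

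- model-based SE = √[(1/m + α)·K]
- true SE ≈ √[(v/m²)·K]

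At α = 0 their ratio is √(m/v). Results with no true cohort difference:

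| μ, a (assumed) | m | v | Model SE | True SE | Ratio | Null rejection at nominal 5% |
|---|---|---|---|---|---|---|
| 0.1, 0.5 | 1.08 | 0.08 | 0.141 | 0.039 | 3.7 | 0% |
| 0.3, 0.5 | 1.23 | 0.27 | 0.132 | 0.062 | 2.1 | 0% |
| 1, 0.5 | 1.80 | 1.26 | 0.109 | 0.089 | 1.2 | 1.8% |
| 4, 1 | 5.0 | 20 | 0.118 | 0.132 | 0.89 | 9.0% |
| 8, 2 | 10.6 | 152 | 0.147 | 0.167 | 0.88 | 8.5% |

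The SEs in the first row come from the formulas. Rows two to five are simulations of 400 replicates.

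- *Rare counts.* In row two the formulas give √(0.02144/1.23) = 0.132 and √(0.27/1.23² × 0.02144) = 0.062, the same as the simulation. Dispersion sat at zero in 94% of those fits. The fitted Poisson then puts e^(−1.23) = 29% probability on a count that cannot occur.
- *High counts.* The simulated SEs are 11% and 12% too small. The formulas, with the median fitted α of 0.444 and 0.917, give 10% and 14%. Repeat simulation at mean positive counts of 5 to 10 gave 9 to 17%, with 8 to 10% rejection. The simulated SD has a relative error of about 1/√800 = 3.5%, so these figures are approximate.

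**What robust SEs do.** With robust SEs, null rejection in rows two to five was 5.0 to 6.3%, and 4 to 7% in repeat runs. With a true latent rate ratio of 1.5, the ordinary fit gave log ratios of 0.090, 0.213 and 0.336, against true log ratios of means among positives of 0.092, 0.213 and 0.336. So it estimates the mean ratio among users without material bias; it is the model-based SE that fails.

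**Combined effect.** Per-patient mean = P(any use) × mean among users. Taking the rates in 9.5 for part one, LMWH over apixaban is 6.483/4.362 = 1.486. With assumed part-two ratios:

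- 1.0: 1.486 × 1.0 = 1.49
- 0.8: 1.486 × 0.8 = 1.19
- 0.673: 1.486 × 0.673 = 1.00

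The same part-one result fits anything from a 49% excess to no difference per patient. The two separate coefficients supply no interval for the product.

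**The case against.** Several stronger readings are tempting, and the documents do not support them.

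- *The plan prescribes an ordinary negative binomial.* It does not. The wording "an appropriate regression model such as a GLM model for costs" makes the named models examples, and a truncated negative binomial is not excluded. The defect is under-specification. It remains true that this is the only model named for positive counts.
- *The plan's standard errors are wrong.* That follows only if model-based SEs are used, and 9.7 names no estimator. Naming a robust SE largely removes the problem without changing the model.
- *The plan gives no per-patient comparison.* It does: 9.3.2 and 9.3.3 report event-related HCRU and costs over all patients, and 9.7 compares the weighted means by t-test. What is unstated is the combined, covariate-adjusted estimate from the regression that 9.7 says will measure the treatment effect.
- *The error is always large.* The multiples near 4 need mean positive counts close to 1. That suits repeat event hospitalizations, but less so the visits, laboratory tests and radiology that 9.3.3 also counts. Where intervals are too wide the error is conservative, and part two then carries little information anyway.
- *Comparing cohorts among patients with an event is itself a defect.* It is a feature of every two-part model, including a hurdle model, and is a further reason to report the combined effect.

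Reach is also limited. HCRU is a secondary objective, and 9.7 caps the multivariable models at four, still to be agreed, so event-related HCRU may not be modelled at all. These points narrow the concern. They do not remove the missing variance estimator or the missing combined estimate, and the latter also touches a primary objective.

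**Conclusion.** The concern holds in this limited form. If the negative binomial in 9.7 is fitted to positive counts without truncation and with model-based SEs, second-part intervals are about 1.2 to 4 times too wide at mean positive counts of about 1.1 to 1.8, and about 10 to 17% too narrow at means of about 5 to 10. These sizes rest on assumed count distributions, on 78 and 116 event patients derived from the recurrent VTE rates in 9.5, and on unweighted data without covariates. Bleeding outcomes may have different numbers.

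The lack of a combined effect needs no assumption: 9.7 describes no step from the two parts to an adjusted mean, difference or ratio per patient, for HCRU or for costs. The truncation problem does not apply to costs, where the second part would be a GLM for positive amounts. This should be settled before analysis.

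**What to change.** Amend 9.7 as follows.

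1. For positive HCRU counts, either specify a zero-truncated negative binomial, or keep the negative binomial with robust SEs. A one-part weighted count model over all patients, with a follow-up offset and robust SEs, is an acceptable alternative. State the variance estimator and how follow-up time enters the model.
2. If the truncated model is chosen, convert its latent mean to the mean among positives before combining: μ/(1−p₀). Its coefficient is the latent rate ratio, not the ratio of means among users.
3. For event-related HCRU and costs alike, report the combined marginal mean per patient in each cohort and the difference. Give an interval from a bootstrap that resamples patients and re-estimates the IPTW weights in each sample. Show the two separate parts as supporting results.

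The cost is a few sentences in 9.7 and modest extra programming. No new data are needed.

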- To compare HCRU associated with recurrent VTE, major bleeding, and CRNM bleeding among VTE patients with cancer treated with apixaban vs LMWH

Study design

A retrospective database analysis will be conducted using IQVIA's PharMetrics® Plus database among newly diagnosed VTE patients with active cancer who received apixaban or a LMWH on or within 30 days following the VTE diagnosis. The analysis will be conducted using data from 01 January 2016 through 31 December 2021 (i.e., the *study period*), including a 12-month pre-index period and 1-month post-index period and patients will be followed through the earliest of the following: health plan disenrollment, index therapy discontinuation, switch to another anticoagulant or end of study period.

Population

Adult patients with evidence of cancer and newly diagnosed VTE, followed by a claim of apixaban or LMWH will be identified. The date of the first apixaban or LMWH prescription will be termed as the index date and two cohorts will be identified based on this index prescription. Patient will be continuously enrolled during the 12-month pre-index period and with a variable post-index period. Other exclusion criteria will also be applied such as patients with evidence of atrial fibrillation, mechanical heart valve, inferior vena cava filter, antiphospholipid syndrome, pregnancy and with any data quality issues.

Variables*Exposures and explanatory variables in the pre-index period or on index date:*

- Demographic characteristics
- Clinical characteristics
- Baseline HCRU and costs

Outcomes

- All-cause HCRU and costs
- Recurrent VTE related HCRU and costs
- Major bleeding related HCRU and costs
- CRNM bleeding related HCRU and costs

Data sources

IQVIA's PharMetrics® Plus database comprises adjudicated claims for more than 190 million unique enrollees across the United States (US). Enrollees with both medical and pharmacy coverage in 2020 represented 40 million lives. PharMetrics Plus has diverse representation of

PFIZER CONFIDENTIAL

CT24-WI-GL02-RF02 4.0 Non-Interventional Study Protocol Template For Secondary Data Collection Study 01-Jun-2022

Page 9 of 35

090177e19b7d94e0\Approved\Approved On: 29-Aug-2023 01:40 (GMT)

Apixaban

B0661183 NON-INTERVENTIONAL STUDY PROTOCOL

Protocol Version: 2.0 29 July 2022

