9.3.1. Baseline Measures

Baseline demographic/clinical characteristics will be descriptively reported for the Apixaban and LMWH cohorts, both pre- and post-IPTW. Demographic characteristics will be measured as of the patient's index date while clinical characteristics will be measured over the 1-year pre-index baseline period.

Demographic Characteristics

- Age (mean, standard deviation [SD], median, interquartile range [IQR])
- Age group (18-24, 25-34, 35-44, 45-54, 55-64, 65-74, ≥ 75 years; n, %)
- Gender (male, female, unknown/missing; n, %)
- Geographic region (Northeast, Midwest, South, West, unknown/missing; n, %)
- Payer type (commercial, Medicaid, Medicare Risk, self-insured, other/unknown; n, %)
- Health plan type (consumer directed health care, health maintenance organization [HMO], indemnity, point-of-service [POS], preferred provider organization [PPO], other/unknown; n, %)

PFIZER CONFIDENTIAL

CT24-WI-GL02-RF02 4.0 Non-Interventional Study Protocol Template For Secondary Data Collection Study 01-Jun-2022

Page 19 of 35

090177e19b7d94e0\Approved\Approved On: 29-Aug-2023 01:40 (GMT)

Apixaban

B0661183 NON-INTERVENTIONAL STUDY PROTOCOL

Protocol Version: 2.0 29 July 2022

- Index date year (2017, 2018, 2019, 2020, 2021; n, %)
- Follow up duration in months (mean, SD, median, IQR)
 - Patients censored due to switching (n, %)
 - Patients censored due to discontinuation (n, %)

Clinical Characteristics

- Prescriber physician specialty (associated with the visit on or closest to the index date, as available) (n, %)
 - Primary care physician (PCP - general practice/family practice/internal medicine)
 - Cardiologist
 - Oncologist
 - Others
 - Unknown/missing
- Index VTE event setting (n, %)
 - Inpatient
 - Total inpatient cost of index VTE hospitalization (mean, SD, median)
 - Length of stay (LOS) of index hospitalization (mean, SD, median)
 - Outpatient
 - Note: Qualifying outpatient encounters followed by qualifying inpatient encounters within 7 days will be considered an inpatient VTE event, unless LMWH or apixaban was initiated between encounters, in which case it will be classified as an outpatient VTE event
- Index VTE type (n, %)
 - DVT
 - PE
 - DVT and PE
- Charlson Comorbidity Index (CCI, Dartmouth-Manitoba adaptation excluding cancer; continuous and categorical [0-1, 2, 3, 4+]) (n, %)
- NCI comorbidity index (continuous and categorical [0-1, 2, 3, 4+]) (n, %)
- Comorbidities of interest (ICD-10 diagnosis codes; n, %)

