090177e19b7d94e0\Approved\Approved On: 29-Aug-2023 01:40 (GMT)

PFIZER CONFIDENTIAL

CT24-WI-GL02-RF02 4.0 Non-Interventional Study Protocol Template For Secondary Data Collection Study 01-Jun-2022

Page 22 of 35

Apixaban

B0661183 NON-INTERVENTIONAL STUDY PROTOCOL

Protocol Version: 2.0 29 July 2022

- Cancer type (n, %)
 - Hematologic cancers
 - Leukemia
 - Lymphoma
 - Multiple myeloma
 - Non-hematologic cancers
- Cancer related treatments (n, %)
 - Chemotherapy
 - Hormone therapy
 - Immunotherapy
 - Radiation
 - Cancer related surgery
- Modified VTE Khorana Risk Scale¹⁰ (n, %)
 - Very high risk (brain, stomach, and pancreas)
 - High risk (lung, lymphoma, gynecologic, bladder, testicular and renal cell carcinoma)
 - Other cancers

Baseline HCRU and costs

- Patients with a pre-index hospitalization (n, %)
- Patients with a pre-index emergency room (ER) visit (n, %)
- Patients with a pre-index outpatient physician office visit (n, %)
 - Number of pre-index outpatient physician office visits (mean, SD, median, IQR)
- Total all-cause healthcare costs (mean, SD median, IQR)
 - Inpatient
 - Outpatient medical
 - ER
 - Pharmacy

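### Outcome-model covariates are kept by a stepwise SMD ≥ 0.10 rule, which measures cohort imbalance and not prediction of cost, and no listed covariate captures metastatic disease

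*Combined protocol and SAP*

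**What the plan says.** On candidates for the outcome models, Section 9.7 (Data analysis) says: "Covariates to be considered for inclusion into the models will include demographic and clinical characteristics of interest guided by the univariate findings". It then says: "These candidate variables will be considered and retained in the model if significant". A bracket equates significance with an SMD of at least 0.10, and selection is stepwise.

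The same section defines the measure: "SMD is calculated as the difference in means or proportions of a variable divided by the pooled standard deviation". SMDs are computed before and after weighting, and the retention sentence does not say which set it uses.

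Confounding is handled first by stabilized IPTW, with regression on top (Sections 9.3 and 9.7). All-cause cost may be analyzed by a weighted gamma GLM, and event-related costs and utilization by two-part models. The propensity-score covariates are not listed.

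Section 9.3.1 collects pre-index cost under a heading of its own, apart from the demographic and clinical lists. The abstract places baseline HCRU and costs under "Exposures and explanatory variables in the pre-index period or on index date".

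For the cancer itself, Section 9.3.1 lists site, hematologic or not, treatment, and a VTE risk scale defined by tumor site. The CCI is specified as "Dartmouth-Manitoba adaptation excluding cancer". An NCI comorbidity index is listed without its items. Stage and metastasis appear nowhere.

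**The concern.** A covariate earns its place in a cost regression by predicting cost. An SMD says only how far two cohorts differ on it, and it is not a significance test. It also does not change as other variables enter a model, so a stepwise procedure driven by SMD is not well defined.

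Both readings of the rule lose precision. If the SMD is taken before weighting, strong cost predictors that happen to be balanced are dropped. If it is taken after weighting, the better the weighting works, the fewer covariates survive. The affected models estimate the all-cause cost ratio and the event-related costs, which serve the primary objectives.

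Disease extent is a separate matter. Metastatic status plausibly influences both the choice of anticoagulant and the cost of care. A variable that is not in the plan cannot be balanced or adjusted for directly, and Section 9.9 does not mention residual confounding.

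**Working it through.** **1. The plan's own figures.** Section 9.5 sizes the study on recurrent VTE and gives nothing for cost. With pooled variance, two-sided 5%, 80% power and no continuity correction,

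n = [1.960·√(2p̄(1−p̄)) + 0.842·√(p₁(1−p₁)+p₂(1−p₂))]² / (p₁−p₂)².

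- 148/3,393 versus 396/6,108 gives 1,788 per cohort (stated: 1,788).
- 5.6% versus 7.9% gives 1,867 per cohort (stated: 1,867).

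Both reproduce. They are used below only for sample sizes and event counts. The documents give no cost variance, no explained variance and no metastasis prevalence, so **every effect size in steps 2 to 4 is an assumption**.

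**2. Precision, by formula.** Covariates explaining a share R² of cost variance multiply the SE of the log cost ratio by √(1−R²). With an assumed cost CV of 2.0 and 1,867 per cohort, the unadjusted SE is √(2·2.0²/1,867) = 0.0655. The ratio detectable with 80% power is exp(2.80·0.0655) = 1.201.

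| R² (assumed) | SE reduction | Detectable ratio |
|---|---|---|
| 0 | – | 1.201 |
| 5% | 2.5% | 1.196 |
| 10% | 5.1% | 1.190 |
| 20% | 10.6% | 1.178 |
| 30% | 16.3% | 1.166 |

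**3. Precision and bias, by simulation.** The model was a stabilized-IPTW gamma/log GLM with 3,600 patients, 300 replicates and a true cost ratio of 1.0. Assumed log-cost slopes were 0.2 per SD of a listed clinical covariate, 0.4 per SD of log baseline cost, and 0.5 for metastatic disease (45% prevalence, independent of the other two).

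| Metastasis SMD | In the weights | In the GLM, besides treatment | Cost ratio | Empirical SE |
|---|---|---|---|---|
| 0 | clinical | clinical | 0.963 | 0.0457 |
| 0 | clinical, baseline cost | none | 0.999 | 0.0473 |
| 0 | clinical, baseline cost | baseline cost | 1.001 | 0.0427 |
| 0.10 | clinical, baseline cost | baseline cost | 0.978 | 0.0437 |
| 0.20 | clinical, baseline cost | baseline cost | 0.953 | 0.0430 |
| 0.20 | all three | all three | 1.002 | 0.0399 |

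- Rows 2 and 3: with baseline cost already in the weights, adding it to an otherwise empty outcome model cuts the SE by 1 − 0.0427/0.0473 = 9.7%. Neither estimate is biased.
- Row 1: bias from baseline cost (3.7%) appears only when it is missing from the weights as well.
- Rows 4 and 5: omitting metastatic disease leaves a bias of 2.2% at SMD 0.10 and 4.7% at SMD 0.20, even with baseline cost fully adjusted. Monte Carlo error is about 0.044/√300 = 0.0025.

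**4. Hand check on metastasis.** For an omitted binary covariate that multiplies cost by R, the bias factor is (1+p₁(R−1))/(1+p₀(R−1)). With R = 1.5:

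- 47.5% versus 52.49% (SMD 0.10) gives 1.2375/1.2625 = 0.980.
- 40% versus 50% (SMD 0.20) gives 1.20/1.25 = 0.960.

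Over R = 1.3 to 2.0 the bias is 1.3% to 3.3% at SMD 0.10 and 2.6% to 6.7% at SMD 0.20.

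**5. Room for covariates in the two-part models.** The second part uses only patients with positive event cost. At the protocol's rates and minimum sizes, recurrent VTE gives 1,788 × (0.04362 + 0.06483) ≈ 194, or 1,867 × (0.056 + 0.079) ≈ 252 patients in both cohorts together. An illustrative set of 35 parameters would leave 5.5 to 7.2 patients per parameter.

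**The case against.** The strongest defense is that the outcome regression is not the main control for confounding. Stabilized IPTW is, and Section 9.3 aims it at measured confounders, which could include baseline cost. This stands. A reader might infer that the retention rule itself leaves the cost ratio confounded, but with baseline cost in the weights the simulated ratio is 0.999. Confounding by baseline cost arises only if it is also missing from the propensity score, whose covariates the plan does not list.

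A reader might also infer that the plan excludes baseline cost. It does not. The candidate sentence is not worded as exhaustive, and the abstract calls baseline HCRU and costs explanatory. The text is silent on whether they enter the models.

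Nor do the documents support a claim that stepwise selection makes the confidence intervals too narrow. That problem usually comes from selection on the outcome, whereas this rule selects on cohort imbalance.

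A double-digit bias from metastatic disease is not supported either. It would need something like 60% versus 40% (SMD 0.20/√0.24 ≈ 0.41) remaining after weighting, together with a doubling of cost.

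Finally, the near-empty model follows only if the SMD is post-weighting. The reference to univariate findings may point to pre-weighting values, in which case balanced predictors are still lost. The code lists and table shells are separate files (Annex 1) and were not available, so a metastasis code list may exist there.

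**Conclusion.** The point holds in two parts.

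- The SMD retention rule uses the wrong criterion for an outcome model on either reading. The cost is mainly precision: about 10% of the SE in the simulation, and 2.5% to 16.3% for R² of 5% to 30%.
- Metastatic disease is in no listed covariate set, so it cannot be adjusted for directly. The illustrative bias in the cost ratio is about 2% to 5% at SMD 0.10 to 0.20.

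All these sizes rest on assumed effects. The metastasis figures further assume that the imbalance is not reduced by weighting on site, treatment and the other listed covariates. To the extent that these carry information on disease extent, the bias would be smaller.

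This should be changed before the analysis. It does not by itself invalidate the comparison.

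**What to change.** 1. Delete the stepwise SMD rule. Use the SMD only to check balance after IPTW.
2. Prespecify the propensity-score covariates as the full set of baseline measures in Section 9.3.1, plus log baseline all-cause cost and a metastatic indicator. Keep the bleeding-risk variables (prior bleeds, thrombocytopenia, anemia, renal disease, peptic ulcer, antiplatelets, NSAIDs), because bleeding-related cost is a primary objective. Leave out follow-up duration and censoring reason: Section 9.3.1 lists them under demographics, but they are observed after the index date.
3. Define the metastatic indicator from secondary-malignancy diagnosis codes up to the index date. The cancer variables now run to 30 days after the VTE encounter, which can fall after treatment has started.
4. Prespecify outcome-model covariates on prognostic grounds, always including log baseline cost and the metastatic indicator.
5. Name a shorter set for the second part of the two-part models, in view of the 194 to 252 recurrent-VTE patients expected at the minimum sizes. One long list for every model would not fit there.

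The cost is a rewritten paragraph in Section 9.7, one extra code list and a few degrees of freedom. No new data source is needed, since diagnosis codes and baseline cost are already in the claims.
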